5. DESIGN AND PROCEDURES

5.1 Study Design

This is a prospective, observational cross-over study that will compare conventional SCS and polymodal SCS during two different time windows during an SCS trial period. Up to 25 patients will be included in the study. Figure 1 illustrates a general diagram of the study process. A screening/enrollment visit will assess the eligibility of a potential subject who has already given adequate time to evaluate and discuss the informed consent form. Patients that meet all the inclusion and exclusion criteria and who reaffirm voluntary informed consent to participate in the study will be enrolled. Patients enrolled in the study will visit the clinic to start the SCS trial period which involves the implantation of the stimulation leads and programming of conventional SCS therapy. Conventional SCS therapy will be administered before PM-SCS therapy for 4 ± 1 days. [REDACTED]

[REDACTED]

[REDACTED]

[figure not shown]

Figure 1. Flow diagram of the study process.

After the patient has trialed conventional SCS therapy, there will be a washout period which is expected to last no more than one day. This will allow analgesic effects of the conventional therapy to wear off. The patient will visit the clinic to crossover to PM-SCS therapy and will trial it for 4 ± 1 days. After the trial period is over, the implanted temporary leads will be disconnected from the ENS and removed from the patient and the trial period will end. The trial period during the study will not extend longer than ten days. Table 2 shows a schedule of events.

Table 2. Schedule of Events.

Event\Activity	Enrollment/ Baseline (Day 0)	Start of SCS Trial (0-30 days after enrollment/baseline)	Crossover to Polymodal SCS (3-5 days after start of trial)	End of Study (3-5 days after crossover to PM-SCS)
Informed Consent	X			
Inclusion/Exclusion Criteria	X			
Pregnancy Test^A	X			
General Health and Pain Medications	X			
Pain NPRS	X		X	X
Informed Consent Reaffirmation	X			
Lead Implantation		X		
X-ray Fluoroscopy		X	X	X
Programming of Conventional SCS and start of trial		[X]		
Programming of PM- SCS			[X]	
Stimulation Sensation Assessment				X
Impression of Improvement and Patient Satisfaction				X
Adverse Event Assessment		X	X	X

^A Administered only to subjects of childbearing potential

[X] Optional reprogramming (conventional or polymodal SCS) visits are allowed at the discretion of the investigator and depending on the feedback from standard of care follow up phone visits.

5.2 Recruitment and Consent:

The investigator will discuss participation in the study with a patient who is already qualified and approved for a SCS therapy trial and who may qualify to be enrolled in the study according to inclusion and exclusion criteria. The patient will be given the opportunity to read an informed consent form (ICF) and get answers to all questions before consenting participation (see Appendix A for details on the Informed Consent Process).

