Trialing of PM modulation therapy in patients with chronic intractable back pain with or without leg pain.
Protocol # [REDACTED]

This page is intentionally left blank

Trialing of PM modulation therapy in patients with chronic intractable back pain with or without leg pain.
Protocol # [REDACTED]

PROTOCOL

Trialing of PM modulation therapy in patients with chronic intractable low back pain with or without leg pain

SGEN-2017PM1

Sponsor:

StimGenics

[name]
[name]

Principal Investigator:

[REDACTED]

Date of Protocol: 24 April 2017

Version: 1.1

*The study will be conducted according to the protocol and in compliance with
Good Clinical Practice and other applicable regulatory requirements.*

This document contains confidential information of StimGenics. Do not copy or
distribute without written permission from the sponsor.

CONFIDENTIAL

PROTOCOL SUMMARY

Study Title: Trialing of PM modulation therapy in patients with chronic intractable lower back pain with or without leg pain.

Purpose of the study: To determine the feasibility of PM modulation therapy in patients with chronic intractable lower back pain with or without leg pain.

Objective: Demonstrate that spinal cord stimulation using multiple simultaneous waveforms provides pain relief in patients suffering chronic intractable low back pain with or without leg pain.

Trial design: This is a prospective, open label, observational cross-over study in which pain relief from a PM modulation therapy, polymodal spinal cord stimulation (PM-SCS), will be compared to conventional spinal cord stimulation. Up to 25 patients will be included in the study. Standard evaluation phase to test the subject's response to commercial SCS system will be conducted for 4 ± 1 days. After a washout period of up to 1 day, polymodal spinal cord stimulation therapy (PM-SCS) will be applied after conventional spinal cord stimulation (SCS) therapy for 4 ± 1 days.

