Treatment: Enrolled patients will receive polymodal SCS therapy after receiving conventional SCS as part of their therapy trial period. Polymodal stimulation will utilize two trial leads (with eight electrodes each), which have been implanted in the epidural space following standard clinical practices and as part of a standard spinal cord stimulation trial period. Each lead will be connected to the output channel of an external neurostimulation unit (ENS) designed to safely deliver either conventional or polymodal electrical signals to the leads. During conventional SCS, arrays of electrodes in the leads will be set to deliver conventional parameters that produce paresthesia coverage of the painful area following standard programming protocols. After the conventional SCS therapy trial phase has been completed (4 ± 1 days), there will be a washout period of up to one day before the patient crosses over to polymodal SCS therapy, which will be administered for 4 ± 1 days. [REDACTED]

[REDACTED]

[REDACTED]

The patient will be educated and trained on operation of a remote controller that allows the patient to operate the ENS and stimulation therapy programs available within. The patient will

also be instructed on troubleshooting both the ENS and remote controller (i.e. changing batteries, etc.).

Pain relief will be assessed in terms of the level of pain before SCS therapy and in comparison with level of pain when conventional SCS and polymodal SCS were trialed.

Primary endpoint:

1. Back Pain reduction relative to baseline pain (i.e. prior to SCS) at day 5 post-initiation of a particular SCS therapy (conventional or polymodal).

Inclusion Criteria:

1. Capable of giving written informed consent to participate in this clinical study based on voluntary agreement after a thorough explanation of the patient's participation is provided to them.
2. Chronic intractable pain of the lower back equal to or greater than pain in lower limbs, and that has been refractory to conservative therapy for ≥ 3 months.
3. Must be older than 18 years old.
4. Average back pain intensity of ≥ 5 out of 10 on the numerical pain rating scale (NPRS).
5. Appropriate candidate for spinal cord stimulation trial.
6. Subjects must be on a stable dose of pain medication regimen for at least one month.

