Programming with PM-SCS will occur during the trial stage period after the patient has undergone a trial of the therapy using conventional SCS. PM-SCS will utilize the same trial leads, interface trial cable, and remote controller that had been used during the conventional SCS period. The leads, interface trial cable and remote controller are commercial products (i.e. FDA approved). The ENS for PM-SCS is an investigational device based on a commercial platform which has been modified and tested to safely provide programs and therapy groups with the proper parameter sets (F, PW, A). The patient will try conventional SCS therapy at the beginning of the trial stage period for up to five days and then, after a brief washout period, will receive PM-SCS therapy for up to five days.

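### Every patient has conventional SCS first and PM-SCS second, so the planned comparison of the two therapies cannot be separated from order; the washout text also needs reconciling

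*Combined protocol and SAP*

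**What the plan says.** **Order.** The Protocol Summary introduces the design thus: "This is a prospective, open label, observational cross-over study". Only one sequence is described. Section 5.1 states "Conventional SCS therapy will be administered before PM-SCS therapy for 4 ± 1 days", and section 1.3 agrees: "Programming with PM-SCS will occur during the trial stage period after the patient has undergone a trial of the therapy using conventional SCS". No second sequence or randomised order appears in the visible text.

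**Comparison.** The Protocol Summary says that "polymodal spinal cord stimulation (PM-SCS), will be compared to conventional spinal cord stimulation", and that pain relief will be judged against the level before SCS and "in comparison with level of pain when conventional SCS and polymodal SCS were trialed". Section 5.1 calls the trial an "observational cross-over study that will compare conventional SCS and polymodal SCS during two different time windows". Section 6.1 plans an analysis of variance, with each patient as own control. It names no period or carry-over term and warns that power and significance may be inadequate.

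**Primary endpoint.** Section 3.3 defines it as the reduction in back pain score from the pre-SCS baseline, taken separately for each therapy.

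**Washout.** Section 5.1 says that after conventional SCS "there will be a washout period which is expected to last no more than one day", and then continues: "The patient will visit the clinic to crossover to PM-SCS therapy and will trial it for 4 ± 1 days". It caps the whole trial period at ten days. Section 5.4.1 sets the crossover visit 4 ± 1 days after initial programming. Section 5.5 describes the conventional pain score, the x-ray check and PM-SCS programming at that visit, and only afterwards mentions an interval of at most one day without therapy.

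**The concern.** A cross-over supports a comparison of treatments because different patients receive them in different orders, which lets a period effect be estimated and removed. With one order only, anything that differs between the first and second windows becomes part of the apparent therapy effect. The protocol itself supplies candidates: time since lead implantation, possible lead repositioning at the crossover visit (section 5.5), and experience with the remote controller. Residual relief from conventional SCS would add to these. Using patients as their own control removes stable differences between patients but none of these.

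At stake is how the PM-SCS minus conventional difference is reported. If it is presented as the effect of the new therapy, it carries a bias that the plan does not acknowledge. The caveat in section 6.1 is about imprecision. Order confounding is a bias, and more patients would not reduce it.

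The washout is the protocol's only stated safeguard against carry-over, so its place in the schedule matters. If the average pain score for a period takes in stimulation-off time, the therapy whose window contains that time is affected.

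**Working it through.** **1. What the contrast estimates.** Let patient *i* have own level m_i, therapy effects C (conventional) and P (PM-SCS), period effects p1 and p2, and carry-over k from conventional SCS into the second window.

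- First window: E(Y_i1) = m_i + C + p1
- Second window: E(Y_i2) = m_i + P + p2 + k
- Difference: E(Y_i2 − Y_i1) = (P − C) + (p2 − p1) + k

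The patient term cancels and the other terms do not. The expression does not involve the number of patients.

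**2. Can any model separate them?** The check is the rank of the within-patient design matrix with 25 patients (the maximum in section 5.1) and two windows each.

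| Effects fitted besides the 25 patient effects | Columns | Rank, fixed order |
|---|---|---|
| Therapy | 26 | 26 |
| Therapy, period | 27 | 26 |
| Therapy, period, carry-over | 28 | 26 |

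Adding period and carry-over leaves the rank unchanged, because in this design the three columns are identical. No analysis of variance on these data can separate them.

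**3. Illustration of size.** The plan gives no SD, alpha, test or success rule, so it has no figure to reproduce. Everything in this step is assumed: a paired t-test, two-sided 5%, SD of the within-patient difference from 1.5 to 3.0 NPRS points, net period-plus-carry-over shift of 0.5 or 1.0 point, and no true therapy difference. The non-centrality is shift ÷ (SD/√n). For n = 25, SD 1.5 and shift 0.5 it is 0.5 ÷ (1.5/5) = 1.667, and the non-central t distribution with 24 degrees of freedom gives a probability of 0.360.

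| n | Shift | SD 1.5 | SD 2.0 | SD 2.5 | SD 3.0 |
|---|---|---|---|---|---|
| 25 | 0.5 | 0.360 | 0.225 | 0.161 | 0.126 |
| 25 | 1.0 | 0.892 | 0.670 | 0.484 | 0.360 |
| 20 | 0.5 | 0.294 | 0.186 | 0.136 | 0.109 |
| 20 | 1.0 | 0.807 | 0.565 | 0.397 | 0.294 |

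The rows for 20 patients are included because 25 is a maximum. The shift may run either way, so it could create a difference or hide one.

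**4. Washout placement.**

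- Section 5.1 narrates conventional SCS, washout, clinic visit, PM-SCS.
- Sections 5.4.1 and 5.5 narrate 4 ± 1 days of conventional SCS, clinic visit (pain score, x-ray, PM-SCS programming), time off, PM-SCS. The visit is 4 ± 1 days after initial programming and also follows 4 ± 1 days of therapy, so on a literal reading no washout fits before it.

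**5. Day count.** Each therapy lasts 3 to 5 days and the washout 0 to 1 day.

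- Washout added to both therapy periods: 3 + 0 + 3 = 6 days at least, 5 + 1 + 5 = 11 days at most. In whole days, 11 is the only total above ten.
- Washout inside the visit windows of Table 2: 3 + 3 = 6 to 5 + 5 = 10 days, within the limit. A one-day washout would then leave 2 to 4 days on one therapy, against the stated 3 to 5.

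**The case against.** The strongest reply is that little depends on the comparison. The stated purpose is feasibility, the objective is that multi-waveform SCS relieves pain, and the primary endpoint is change from baseline under each therapy. No superiority hypothesis or success rule is visible. The order is openly declared, and section 6.1 describes an early-stage observational study. This stands as a limit on weight: a reader might infer that the primary endpoint is invalid, and the documents do not support that, since it needs no contrast between therapies. It does not dispose of the point, because the protocol says more than once that the therapies will be compared and nowhere says that order confounds the result.

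A reader might also infer that the bias favours PM-SCS. Nothing in the documents fixes its direction. Expectation attached to a new, open-label therapy is a real and separate bias, but it belongs to the lack of blinding and would largely persist if the order were randomised.

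On the washout, the objection has more force. The placement in section 5.1 is read from sentence order. Redacted text follows the design description there and in the Protocol Summary, Figure 1 is not shown, and the appendices are redacted. Most of the visible text fits one sequence if crossing over means the start of PM-SCS. A flat contradiction is therefore not established. Nor is it established that off-time counts against either therapy: section 6.1 takes as endpoint of record the average score reported at the end of each therapy period, and section 5.5 describes the crossover score as the pain level obtained with conventional SCS. For the PM-SCS average, the visible text leaves open whether off-time is included. Finally, the ten-day limit can be read as already ruling out the 11-day case.

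**Conclusion.** The fixed-order point holds with high confidence and depends on no assumed number. The PM-SCS minus conventional difference is fully aliased with period and carry-over, and the caveat about power does not cover this. The endpoint of change from baseline remains reportable under each therapy, but it is uncontrolled.

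The size of the bias in this trial is unknown. For 25 patients the illustrative false-positive range is 13% to 36% for a 0.5-point shift and 36% to 89% for a 1.0-point shift. It rests wholly on the assumed SDs, shifts, test and alpha, and shows only that modest shifts would matter.

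The washout point holds with moderate confidence, and only as a request to reconcile sections 5.1, 5.4.1 and 5.5 with Table 2 and the ten-day limit. The redacted text or Figure 1 may already do so; they would not change the stated order.

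**What to change.** 1. In sections 5.1 and 6.1, limit the conclusion to change from baseline under each therapy, stated as uncontrolled. Label the PM-SCS minus conventional difference as descriptive and confounded with order.
2. Reconcile sections 5.1, 5.4.1 and 5.5 on when the washout falls relative to the crossover visit and its NPRS score, and reconcile these with the Table 2 windows and the ten-day limit. Record the actual washout duration for each patient. Make clear that the average NPRS for each therapy period treats stimulation-off time in the same way.

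Both are wording changes plus one recorded duration, with no extra patients or visits. The price is a weaker comparative claim.

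Randomising the order is not part of this fix. It would make the period effect estimable but would still rely on the washout for carry-over. It also involves a trade-off, because section 2.2 ties eligibility for a permanent implant to the outcome of the conventional trial.

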3. OBJECTIVES

3.1 Purpose:

To determine the feasibility of polymodal spinal cord stimulation therapy in patients with chronic intractable lower back pain with or without leg pain.

3.2 Objective:

To demonstrate that spinal cord stimulation using multiple simultaneous waveforms provides pain relief in patients suffering chronic intractable low back pain with or without leg pain.

3.3 Primary endpoint:

3.3.1 Back pain score reduction relative to baseline pain score (i.e. prior to SCS) at day 5 post-initiation of a particular SCS therapy (conventional or polymodal).

[REDACTED]

[REDACTED]

[REDACTED]

[REDACTED]

[REDACTED]

[REDACTED]

[REDACTED]

[REDACTED]

[REDACTED]

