Following a satisfactory demonstration on ENS and remote controller operation, the patient will be discharged to home with an emergency 24-hour contact information should the patient have any issues or questions. Programming and training procedure should be approximately 1.5 to 2 hours long. The patient will be scheduled to return to the clinic for the crossover reprogramming visit 4 ± 1 days after the initial programming.

5.5 Clinic Visit 3: Crossover visit:

After 4 ± 1 days of trialing conventional SCS therapy, the patient will return to the clinic for a reassessment of the lead location using x-ray fluoroscopy, and crossover to PM-SCS therapy. Pain level obtained with conventional SCS will be assessed and recorded in CRF05 before crossing over to PM-SCS therapy. The study physician may reposition the leads if deemed necessary upon comparison to the initial x-ray image. If leads have migrated and cannot be re-adjusted, the patient will be exited from the study and subject data will be excluded from the final analysis. After x-ray assessment, stimulation parameters will be programmed as described below for PM-SCS. No therapy will be given for up to one day to allow washout of the conventional SCS therapy.

5.5.1 Polymodal SCS Therapy:

In this case the ENS will be programmed to deliver multiple simultaneous signals with different stimulation parameters to different electrode arrays in the leads. Stimulation signals will be in the 20-1,200 Hz range and a maximum pulse width of 1 ms, which is within the CE Mark and FDA approved parameters. The parameters of each program will be saved in the remote controller. The patient will be educated and trained on operation and troubleshooting the ENS and remote controller as it pertains to PM-SCS therapy.

5.6 Standard of Care Follow up phone visits:

It is standard practice that during a SCS trial period, a Clinical Field Technician (CFT) will contact the patient by phone to track the status of therapy and comfort of the patient.

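### The ten-day cap, the day-5 primary endpoint and the position of the washout contradict one another, so the timing of the primary comparison is not settled

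*Combined protocol and SAP*

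**What the plan says.** All references are to the combined protocol and SAP.

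- **Capped period.** Under 5.1, patients "start the SCS trial period which involves the implantation of the stimulation leads and programming of conventional SCS therapy". At the other end, "the implanted temporary leads will be disconnected from the ENS and removed from the patient and the trial period will end". Between these two events, "The trial period during the study will not extend longer than ten days".
- **Therapy periods.** Section 5.1 states: "Conventional SCS therapy will be administered before PM-SCS therapy for 4 ± 1 days". It gives PM-SCS the same 4 ± 1 days. Section 1.3 describes conventional SCS "for up to five days and then, after a brief washout period, will receive PM-SCS therapy for up to five days". The order is the same for every patient.
- **Washout.** The summary and 5.1 place it after conventional SCS and before the crossover to PM-SCS. It has an upper limit of one day and no minimum. Section 5.5 first has the crossover visit, with the conventional pain score, x-ray and PM-SCS programming, and then states: "No therapy will be given for up to one day to allow washout of the conventional SCS therapy".
- **Table 2.** The crossover comes 3 to 5 days after the start of the trial. The last column is headed "End of Study (3-5 days after crossover to PM-SCS"). No column is given to the washout.
- **Primary endpoint.** The summary and 3.3.1 measure back pain reduction "at day 5 post-initiation of a particular SCS therapy (conventional or polymodal"). Section 6.1 instead takes the score at the end of each therapy period as the endpoint of record. It asks patients to rate their average pain over a window between visits.

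**The concern.** The trial's one comparison is within patient: pain on conventional SCS against pain on PM-SCS. It is interpretable only if both scores are taken at a comparable, defined time on stimulation. The cap, the windows, the washout and the endpoint definition each bear on that time, and they do not agree.

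Two things are at stake. The day named for the primary endpoint may not exist for some patients who follow the protocol. And an off-therapy day may be charged to one therapy's exposure and pain recall but not to the other's. Because conventional SCS always comes first, such an imbalance would run in the same direction in every patient handled that way. It could not be averaged out as it could with randomised order.

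**Working it through.** **Inputs.** Conventional SCS C = 3 to 5 days, washout W = 0 to 1 day, PM-SCS P = 3 to 5 days (summary and 5.1). Cap = 10 days from lead implantation to lead removal (5.1), so the washout lies inside it. Endpoint at day 5 of each therapy (summary, 3.3.1) or at the end of each period (6.1).

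**1. Total against the cap.** Total = C + W + P.

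- Minimum: 3 + 0 + 3 = 6
- Nominal with full washout: 4 + 1 + 4 = 9
- Maximum: 5 + 1 + 5 = 11, which exceeds 10 by one day

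The figure of ten is reproduced as 5 + 5, that is, with the washout zero, uncounted or absorbed in a Table 2 window. In whole days there are 3 × 2 × 3 = 18 combinations. Only 5 + 1 + 5 exceeds the cap; 4 + 1 + 5, 5 + 0 + 5 and 5 + 1 + 4 equal it.

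**2. Can both therapies reach day 5?** The documents do not say how days are counted.

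| Meaning of day 5 | Days needed on each therapy | Largest washout under the cap | Periods that miss it |
|---|---|---|---|
| Five elapsed days | 5 | 10 − 5 − 5 = 0 | 3 and 4 days |
| Fifth calendar day (4 elapsed) | 4 | 10 − 4 − 4 = 2, so the permitted 1 day fits (4 + 1 + 4 = 9) | 3 days |

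On the first reading, 5 days of conventional SCS and a one-day washout leave at most 10 − 5 − 1 = 4 days for PM-SCS. That is inside 4 ± 1 but short of day 5. On either reading, a 3-day period misses day 5 whatever the cap. Under 6.1 that patient still has a score of record, so 3.3.1 and 6.1 define different endpoints for the same patient.

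**3. Where the washout falls.** Suppose Table 2's windows run from visit to visit and the washout lasts one day.

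- *After the crossover visit (5.5):* time on PM-SCS = (3 − 1) to (5 − 1) = 2 to 4 days, against 3 to 5 on conventional SCS. The lower end is below the 3-day minimum implied by 4 ± 1. Five elapsed days of PM-SCS are never reached, and four only at the latest permitted end visit. If the recall window in 6.1 is also visit to visit, the off-therapy day makes up 1/5 (20%) to 1/3 (33%) of the PM-SCS window and none of the conventional one.
- *Before the crossover visit (one reading of the summary and 5.1):* the same arithmetic gives 2 to 4 days on conventional SCS and 3 to 5 on PM-SCS, with the off-day ahead of the conventional score.

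With no interval of its own in Table 2, the washout is charged to one therapy or the other.

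**The case against.** The periods are ranges, and the cap sits in the same section, so it can fairly be read as a joint limit on them. On that reading 17 of the 18 whole-day combinations comply and the nominal schedule has a day to spare. Section 6.1 also guarantees a score whatever the period's length: 5 + 1 + 4 = 10 meets the cap and gives PM-SCS its nominal duration. This is a feasibility study of up to 25 patients, and 6.1 itself concedes limited power. All of this stands, and it limits point 1 to a minor inconsistency.

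Three stronger readings are tempting, and the documents do not support them:

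- *The cap cannot hold the planned schedule.* It fails only when all three periods run at or close to their upper limits.
- *Day 5 on both therapies forces the washout to be dropped.* This needs day 5 to mean five elapsed days. Counting from a Day 0 and in days after an event, as the schedule does, leans that way, but no definition is given.
- *PM-SCS, being last, always gives up the time.* 4 + 1 + 5 = 10 meets the cap by shortening conventional SCS, and no text says which period yields. Likewise, the 2-day PM-SCS figure depends on following 5.5 and counting from the visit. If crossover means the start of PM-SCS, as the summary and 5.1 allow, PM-SCS keeps its 3 to 5 days.

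Figure 1 is not shown, and text next to the duration statements and the appendices is redacted. A clarification may exist there. It would not remove the disagreement between 3.3.1 and 6.1, or between 5.1 and 5.5.

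**Conclusion.** The concern holds as a set of three internal contradictions.

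1. The permitted maxima exceed the cap by one day (11 against 10), at the upper corner only.
2. The day-5 endpoint does not match periods that may end at 3 or 4 days, nor the end-of-period score in 6.1. Under either way of counting, 3-day periods miss it.
3. The washout's position is contradictory and has no interval in Table 2. Following 5.5 and Table 2 with visit-based counting, a full-day washout gives 2 to 4 days on PM-SCS against 3 to 5 on conventional SCS and puts an off-therapy day into the PM-SCS pain average.

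The second and third carry the weight, because they bear on the primary measurement itself. The third rests on a washout of a full day and on windows counted from the crossover visit. Its effect in NPRS points, and even its direction, cannot be derived from the documents. This should be fixed before enrolment, but it does not by itself invalidate a feasibility study.

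**What to change.** Reconcile the summary, 3.3.1, 5.1, 5.5, 6.1 and Table 2:

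- Show the washout as its own interval in Table 2, counted in neither therapy's window, and describe its position the same way in the summary, 5.1 and 5.5.
- Count the PM-SCS window, and the period over which PM-SCS pain is recalled, from PM-SCS switch-on.
- Define how days are counted. Use one primary time point, identical in 3.3.1 and 6.1, that every permitted schedule reaches for both therapies.
- Make the cap and the period limits mutually consistent. Which limit changes is for the sponsor and investigators; no duration is proposed here.
- Record stimulation start and stop times for each therapy, if the forms do not already (they are not available to check), and report days on stimulation per therapy.

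The cost is an amendment to wording and one table (which also appears in the summary), at most a few date and time fields, and slightly less scheduling freedom. No extra visits or patients are needed.
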